
Statistical considerations
	
Given the descriptive nature of the study, results will be reported in terms of precision (95% confidence intervals, CIs) and not statistical power.
 
Data from all centres will be pooled for analysis. Categorical data will be described by the number (n) and percentage (%) of patients in each category. Continuous data will be described by number of observations, mean and standard deviation (SD) for normally distributed data or median and interquartile range for non-normally distributed data, and minimum and maximum values where relevant. Missing and invalid observations will be tabulated as a separate category. Rates will be reported with 95% CIs.

Regulatory, ethical and administrative obligations
	
This is an observational research study where only patients who consent (if living) for their medical records to be accessed for the purpose of the study will be included in the study. For deceased patients study data will be extracted from medical records by a member of the direct care team to preserve patient confidentiality in absence of consent from these patients.
 
There will be no change to the clinical management of patients as a result of taking part in the study. No additional patient investigations or tests will be required.
 
Data collection will be carried out by either the clinical care team at

	
each centre or a pH Associates researcher. Therefore, this study will be submitted for NHS Research Ethics Committee (REC) approval in line with the harmonised edition of the Governance Arrangements for Research Ethics Committees (GAfREC). Local management approval will be obtained via the Health Research Authority (HRA) and Trust/Health Board Research and Development (R&D) departments.
 
All electronic data files will be securely stored on a password-protected internal UK-based server at pH Associates and all study-related documents will be kept in a locked cupboard when not in use. Access to the study database will be restricted (by password protection) and only granted to pH Associates staff who are directly involved with the study.

--	---

5. Study amendments and protocol deviations

All amendments to the protocol will be documented in Table 1. Protocol deviations will be documented in a Protocol Deviation Log.

Table 1. Study amendments

Amendment number	Date of amendment	Description	Reason for amendment

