9.5.1 Primary endpoint

The primary endpoint of this study is the mean maximum tolerated daily dose of RAASi achieved (as percentage of target dose).

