Given the descriptive nature of this study, a preliminary estimation of the required sample size is expressed in terms of precision and not statistical power. It is expected that approximately 100 patients will be sufficient to generate reliable results, as determined by relatively narrow confidence intervals.

Table 3 Confidence limits for different sample sizes and mean doses of RAASi achieved

Mean dose (as % of target dose)	50 patients		100 patients		150 patients	
	LCL	UCL	LCL	UCL	LCL	UCL
90%	82%	98%	84%	96%	85%	95%
80%	72%	88%	75%	85%	76%	84%
70%	63%	77%	65%	75%	66%	74%
60%	54%	66%	56%	64%	57%	63%
50%	45%	55%	47%	53%	47%	53%
40%	34%	46%	36%	44%	37%	42%
30%	23%	37%	25%	35%	26%	32%

LCL – lower confidence limit

UCL – upper confidence limit

The table shows that the reliability of estimates for the mean dose of RAASi achieved (as a percentage of the target dose) improves when the study sample is increased from 50 to 100

patients. This is applicable for relatively small or large percentages of the target dose achieved. Reliability does not improve much more when the sample size is increased from 100 to 150 patients. Therefore, approximately 100 patients will be sufficient to generate reliable results for the primary endpoint. The number of patients in the study will be allocated as follows: 50% (approximately n=50) with CKD and HF and 50% (approximately n=50) with CKD and T2DM. This distribution includes patients with all three conditions: CKD, HF and T2DM.

12. Statistical analysis

Analyses will be performed by pH Associates. Data from all centres will be pooled for analysis. Distributions and descriptive statistics of central tendency (medians and arithmetic means) and dispersion (standard deviation, interquartile range) will be presented for quantitative variables wherever possible. Categorical variables will be described with frequencies and percentages. Ordinal variables will also have medians and interquartile ranges described. 95% confidence intervals will be presented for estimates of proportions and means of distributions.

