- As only patients with 12 months of follow up data will be included in the study, patients who died or were discharged from outpatient care within the follow up period will be excluded. The number of patients affected by this is likely to be small and, consequently, there should be minimal potential bias due to their exclusion from the study.
- Data collected retrospectively will rely on the completeness and quality (including accuracy) of the medical records. The impact of poor quality data has been minimised by robust feasibility testing of the protocol framework during its development and additional evaluation during site selection. Furthermore, training of all data collectors and SDV will ensure consistent data collection and adherence to the study protocol.
- The study sample size may be inadequate to show results with adequate statistical precision, due to differences in patient and/or treatment characteristics in the published studies that were used to guide the choice of sample size.
- There will be inconsistencies in the availability of primary care prescribing data and haematology and biochemistry test results through secondary care computer systems and paper medical records. During study development and set up, study centres with access to the required primary care data will be identified to reduce the potential effects of missing or incomplete data.

15. Pharmacovigilance

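### Table 3 rests on an unstated SD that varies by row and is smallest at a mean of 50%, so that row's precision is optimistic relative to the rest of the table

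*Protocol*

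**What the plan says.** The primary endpoint (section 9.5.1) is a mean: the maximum tolerated daily RAASi dose, expressed as a percentage of target. The synopsis says that "results will be reported in terms of precision (95% confidence intervals, CIs) and not statistical power". Section 11 takes about 100 patients to be enough, "as determined by relatively narrow confidence intervals", and supports this with Table 3. The table prints lower and upper limits for means from 30% to 90% of target at 50, 100 and 150 patients. The text below it says that reliability improves from 50 to 100 patients and adds: "This is applicable for relatively small or large percentages of the target dose achieved". It then concludes: "Therefore, approximately 100 patients will be sufficient to generate reliable results for the primary endpoint".

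Section 11 gives no SD, formula or source for the limits. Section 14 (Study limitations) warns that precision may prove inadequate because of "differences in patient and/or treatment characteristics in the published studies that were used to guide the choice of sample size". Neither section says which studies these were or what spread they reported.

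**The concern.** The width of a confidence interval for a mean depends on the SD and the number of patients, not on the mean itself. In Table 3, however, the half-width at 100 patients is 6, 5, 5, 4, 3, 4 and 5 points for means of 90, 80, 70, 60, 50, 40 and 30%. The SD behind the table must therefore fall towards 50% and rise again on either side. The protocol gives no reason for this.

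The table is the whole argument for the sample size. A reader cannot see that the narrowest interval, in the 50% row, comes from an assumed smaller spread, and cannot check any row against data.

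**Working it through.** **Inputs.** The limits come from Table 3. The 95% level comes from the synopsis, since the table does not print one. The endpoint lies between 0 and 100, because section 9.2.1 admits only patients who stay below target dose.

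**Formula.** Half-width h = 1.96 × SD / √n, so SD = h × √n / 1.96. Limits are printed to whole percents, so each printed h covers h − 0.5 to h + 0.5.

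**Can the table be reproduced from stated inputs?** No, because no SD is stated. The best single SD (about 28) reproduces only 15 of the 42 printed limits. A binomial SD, √(m(100 − m)), reproduces at most 6.

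**Implied SD, 50% row.** Printed half-widths are 5, 3 and 3 at n = 50, 100 and 150.
- n = 50: 4.5 × 7.07 / 1.96 = 16.2 to 5.5 × 7.07 / 1.96 = 19.8
- n = 100: 2.5 × 10 / 1.96 = 12.8 to 3.5 × 10 / 1.96 = 17.9
- n = 150: 2.5 × 12.25 / 1.96 = 15.6 to 3.5 × 12.25 / 1.96 = 21.9
- Consistent with all three: 16.2 to 17.9

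**Implied SD, all rows, by the same method.** The n = 150 upper limits at 40% and 30% are printed as 42% and 32%, which are not symmetric about the mean. The symmetric values 43% and 34% were used instead.

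| Mean (% of target) | Printed half-width at n = 50 / 100 / 150 | SD consistent with all three |
|---|---|---|
| 90 | 8 / 6 / 5 | 28.1-30.7 |
| 80 | 8 / 5 / 4 | 27.1-28.1 |
| 70 | 7 / 5 / 4 | 23.4-27.1 |
| 60 | 6 / 4 / 3 | 19.8-21.9 |
| 50 | 5 / 3 / 3 | 16.2-17.9 |
| 40 | 6 / 4 / 3 | 19.8-21.9 |
| 30 | 7 / 5 / 4 | 23.4-27.1 |

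The range for 50% does not overlap any other row, so rounding is not the cause. With t quantiles the ranges shift slightly (50%: 15.8-17.6; 30% and 70%: 22.9-26.4) and the pattern is the same. The rule SD = max(m, 100 − m)/3, with t quantiles, reproduces 38 of the 42 limits.

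**Plausibility of the shape.** For values between 0 and 100 with mean m, the largest possible SD is √(m(100 − m)).
- m = 90: √(90 × 10) = 30. The table uses about 28-31, close to this ceiling, which would need patients split almost entirely between the two extremes.
- m = 50: √(50 × 50) = 50. The table uses about 17, its smallest value, where there is most room to vary.

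**Half-widths at fixed SDs (1.96 × SD / √n).**

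| SD | n = 50 | n = 100 | n = 150 |
|---|---|---|---|
| 17 | 4.7 | 3.3 | 2.7 |
| 20 | 5.5 | 3.9 | 3.2 |
| 25 | 6.9 | 4.9 | 4.0 |

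At a mean of 50% and n = 100, relative to SD 17, SD 20 widens the interval by 3.92 / 3.33 = 1.18 and SD 25 by 4.90 / 3.33 = 1.47. With SD 25 the limits are 45.1% and 54.9%. Rounded, this is 45%-55%, the interval Table 3 prints for 50 patients.

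At 40% and 60% with n = 100, the printed ±4 agrees with SD 20 (±3.9) and would become about ±5 at SD 25. That lies between the printed ±4 for 100 patients and ±6 for 50.

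**The case against.** The strongest reply is that nothing here shows the 50% row to be wrong. The document gives no true SD. An SD of 17 is possible at a mean of 50%, and the bound of 50 limits the largest spread, not the actual one. This stands: the row can be called optimistic only relative to the table's other rows.

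It is also fair that the effect is narrow. The 40% and 60% rows already agree with SD 20. The 90% row probably errs the other way. A reader might infer that all mid-range rows are overstated, or that 100 patients always give only what is printed for 50. That equality is exact in the 50% row alone.

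A reader might also argue from the start doses in Appendix 1 that the mean will land near 50%. Start doses do not indicate the highest dose reached over 12 months, so this is conjecture. Likewise, the close fit of max(m, 100 − m)/3 suggests a constructed rule but does not prove one, because the published studies mentioned in section 14 are not identified.

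Finally, section 11 calls its estimate preliminary, and section 14 concedes that precision may be inadequate. These caveats soften the claim, but they do not disclose the SD or explain why it changes by row.

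**Conclusion.** The point holds as one of transparency and internal consistency. Table 3 rests on an unstated SD that varies from about 16-18 to about 28-31 across rows, in a shape that is implausible for a bounded percentage. At a mean of 50% and 100 patients, the printed ±3 (about ±3.3 at SD 17) becomes ±3.9 at SD 20 and ±4.9 at SD 25.

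This assumes a 95% normal-theory interval and an SD range of 17-25 read from the table's own rows, since the document offers no other source.

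A reader might infer that 100 patients are too few. The document does not support that. At 100 patients the table already accepts ±5 at means of 30, 70 and 80% and ±6 at 90%, so ±4.9 at 50% is within what the protocol treats as sufficient. The conclusion that about 100 patients suffice is not overturned.

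**What to change.** In section 11, state the assumed SD of the dose as a percentage of target and give its source, naming the published studies that section 14 refers to. Replace Table 3 with half-widths for declared SDs held constant across means. For example, at 50, 100 and 150 patients, SD 20 gives ±5.5, 3.9 and 3.2 points and SD 25 gives ±6.9, 4.9 and 4.0. Recalculation also removes the two asymmetric limits at 150 patients.

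Restate the expected precision, conditional on that SD, as about ±4 to 5 percentage points at 100 patients and about ±5.5 to 7 for each group of about 50. Keep the target of about 100.

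The cost is a rewording of section 11 and its table, with a slightly less favourable figure at a mean of 50%. No further patients and no design change are needed.

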- As only patients with 12 months of follow up data will be included in the study, patients who died or were discharged from outpatient care within the follow up period will be excluded. The number of patients affected by this is likely to be small and, consequently, there should be minimal potential bias due to their exclusion from the study.
- Data collected retrospectively will rely on the completeness and quality (including accuracy) of the medical records. The impact of poor quality data has been minimised by robust feasibility testing of the protocol framework during its development and additional evaluation during site selection. Furthermore, training of all data collectors and SDV will ensure consistent data collection and adherence to the study protocol.
- The study sample size may be inadequate to show results with adequate statistical precision, due to differences in patient and/or treatment characteristics in the published studies that were used to guide the choice of sample size.
- There will be inconsistencies in the availability of primary care prescribing data and haematology and biochemistry test results through secondary care computer systems and paper medical records. During study development and set up, study centres with access to the required primary care data will be identified to reduce the potential effects of missing or incomplete data.

15. Pharmacovigilance

15.1 Reporting procedures for adverse events

As this is a study based on secondary use of data, safety monitoring and safety reporting, where there is a safety relevant result, is provided on an aggregate level only; no reporting on an individual case level is required. In studies based on secondary use of data with a safety relevant result, reports of adverse events/adverse reactions should be summarised in the study report, i.e. the overall association between an exposure and an outcome. Relevant

findings from the study report will be included in the periodic aggregated regulatory reports submitted to Health Authorities.

15.2 Definitions

15.2.1 Adverse events

An adverse event (AE) is any untoward medical occurrence in a patient administered a pharmaceutical product and which does not necessarily have to have a causal relationship with this treatment. An AE can therefore be any unfavourable and unintended sign (including an abnormal laboratory finding, for example), symptom, or disease temporally associated with the use of a medicinal product, whether or not considered related to the medicinal product. The definition of an AE includes worsening of a pre-existing medical condition.

15.2.2 Serious adverse events

A serious adverse event (SAE) is any adverse drug reaction as defined above that:

- is fatal
- is life threatening (places the subject at immediate risk of death)
- requires in-patient hospitalization or prolongation of existing hospitalization
- results in persistent or significant disability/incapacity
- is a congenital anomaly/birth defect
- other significant medical hazard

A serious adverse drug reaction (SADR) is a serious adverse event that is considered related to the medicinal product. A hospitalization meeting the regulatory definition for “serious” is any inpatient hospital admission that includes a minimum of an overnight stay in a healthcare facility. “Other significant medical hazards” refer to important medical events that may not be immediately life-threatening or result in death or hospitalization, but may jeopardize the patient or may require intervention to prevent one of the other outcomes listed in the definition above. Examples of such events could include allergic bronchospasm, convulsions, and blood dyscrasias, drug-induced liver injury, events that necessitate an

emergency room visit, outpatient surgery, or other events that require other urgent intervention.

16. Ethical and regulatory obligations

16.1 Protection of human subjects

This study will comply with all applicable laws, regulations, and guidance regarding patient protection, including patient privacy. As the study will make use of medical records, compliance with the HIPAA Privacy Rule (46 CFR Part 160; Part 164 (subparts a, e)) is required.

To maintain subject confidentiality, no demographic data that could be used to identify the patient will be collected (e.g. name, date of birth). Only gender and the month and year of birth (to calculate age) will be collected. In order to protect patients' identity, a study-specific unique number (study ID) will be assigned to each patient and related study records. Patients' study ID will only be linked to their name and hospital identification number on a patient recruitment log which will remain in the secure custody of the study team at each centre and will not be disclosed to any person outside the centre study team, not even pH Associates staff involved in the study. This log will not leave the corresponding NHS Trust/Health Board and will be the responsibility of the principal investigator at each study centre.

This study will use data available within secondary care, including patient information from primary care that is provided within medical records in secondary care. Permission will not be sought to directly access primary care medical records. Since this observational study relies only on data collected from medical records in secondary care that are anonymised for study use, no risks or benefits to patients participating in the study are expected. Patients will have no direct involvement in the study with the exception of providing their informed consent for data to be collected from their medical records. There will be no change to the management of patients as a result of taking part in the study.

17. Study timelines

The key milestones of this study are shown in Table 4.

Table 4 study timelines

Study milestone	Expected date(s)/frequency
Start of data collection	March 2018
End of data collection	July 2018
Data analysis	July – August 2018
Study progress reports	By telephone every two weeks
Submit final report of study results	September 2018

18. Administrative and legal obligations

18.1 Study amendments and study termination

Amendments must be made only by prior agreement between Vifor Fresenius Medical Care Renal Pharma UK Ltd, pH Associates and [name], Chief Investigator. The Research Ethics Committee (REC) must be informed of all amendments and give approval for substantial amendments. The Chief Investigator must send a copy of the approval letter from the REC to Vifor Fresenius Medical Care Renal Pharma UK Ltd.

pH Associates, Vifor Fresenius Medical Care Renal Pharma UK Ltd, and the investigator reserve the right to terminate participation in the study according to the study contract. pH Associates will notify the REC in writing of the study's completion or early termination and send a copy of the notification to Vifor Fresenius Medical Care Renal Pharma UK Ltd and the Chief Investigator.

18.2 Study documentation and archive

All electronic data files will be securely stored on a password-protected internal, UK-based server at pH Associates and all study-related documents will be kept in a locked cupboard when not in use. Access to the study database will be restricted (by password protection)

and only granted to pH Associates staff who are directly involved with the study. Completed eDCFs will be transmitted in real time over a secure internet connection to pH Associates. The principal investigator (PI) at each centre must ensure that information entered onto the eDCF is traceable to the source documents in patients' medical record (paper or electronic). Changes to the eDCF will be recorded in the MACRO audit trail, including changes in response to data queries, SDV and data entry errors.

18.3 Ethical and regulatory approvals

Data collection may be carried out by either the NHS clinical care team at each centre or pH Associates. Therefore, this study will be submitted for NHS Research Ethics Committee (REC) approval via the Health Research Authority (HRA), in line with the harmonised edition of the Governance Arrangements for Research Ethics Committees (GAfREC)¹¹. NHS management approval for local conduct of the study will be sought through the Research and Development (R&D) department in each participating NHS Trust/Health Board. The study will also be submitted for inclusion in the National Institute for Health Research (NIHR) portfolio of research studies.

18.4 Ethical issues

This is an observational research study where only living patients providing written informed consent will be included in the study and no data collection will take place until written informed consent has been provided (except for deceased patients whose data will be collected by members of the NHS care team to preserve patient confidentiality).

19. Communication of study results

When the study has been completed and the study report is finalised, the results of this observational study may either be submitted for publication and/or posted in a publicly accessible database of results. Publications will comply with Vifor Fresenius Medical Care Renal Pharma UK Ltd's standards and the STROBE (Strengthening the Reporting of OBservational Studies in Epidemiology) checklist for cohort, case-control, and cross-sectional studies (combined checklist)¹².

Authorship of publications arising from the study will follow the guidelines proposed by the International Committee of Medical Journal Editors (2015)¹³.

All authors will have:

- made substantial contributions to conception or design or acquisition of data, or analysis and interpretation of data; AND
- participated in drafting the article or revising it critically for important intellectual content; AND
- approved the final version to be published.

Each author will meet all of these conditions and all individuals meeting these criteria will be authors. Acquisition of funding, collection of data, or general supervision of the research group does not justify authorship. Each author will have participated sufficiently in the work to take public responsibility for appropriate portions of the content. Potential conflicts of interest will be disclosed.

20. Study support

Vifor Fresenius Medical Care Renal Pharma UK Ltd, the study sponsor, have commissioned pH Associates Ltd to develop materials for and co-ordinate the conduct of the study, including protocol development, ethical and local approval, retrospective data collection, analysis and presentation of the results. pH Associates is an independent consultancy specialising in the evaluation of healthcare services and interventions in the NHS through observational research, with a focus on the design and implementation of 'Real World Data' projects in order to understand current NHS practices.

21. References

1. Public Health England. Chronic kidney disease prevalence model. London: Public Health England; 2014.
